Primary Endpoint:	A demonstrable two-fold increase in, or value exceeding 10µg/g of, the concentration of intra-tumoural doxorubicin at the treated tumour site following FUS-induced mild hyperthermia, in at least 50% of evaluable participants.
Secondary Endpoints:	
 Part I only: Achievement of the desired range of mild hyperthermia in the target tissue as monitored by the implanted thermometry device during FUS exposure

	
 2. Persistence of cell viability stain or percentage of cell or tissue necrosis under 30% following FUS exposure, as assessed by cytological or histological methods 3. Significant bone marrow suppression, deranged liver function and liver toxicity. 4. Adverse events up to 30 days post-intervention: 
 a. Deemed related to ThermoDox® b. Deemed related to FUS
Tertiary (Exploratory) Endpoints:	
Regarding doxorubicin released by optimal FUS exposure parameters:
 
 1. Combined analysis of relevant end points to establish most effective alternative analytical method(s) for quantifying drug release: 
 a. Released biopsy samples exhibiting averaged regions of nuclear or background fluorescence levels at least twice that of a suitable control, as assessed by fluorescence microscopy b. Liver MRI/MR-Spectroscopy indicating targeted delivery of doxorubicin to the tumour by demonstrating a statistically significant increase in the tumour:background ratio of signal intensity following intervention compared to baseline c. A significant decrease of in total doxorubicin plasma levels over time-matched clearance levels, following FUS-induced release 2. Radiological evidence of tumour response at timepoints up to 60 days post-intervention in the FUS-targeted tumour and control(s), as assessed by Principles of Choi and RECIST response evaluation using MRI and CT [11, 12] and SUV_{max} using PET-CT [13]

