	
pregnancy test (serum) is required within 30 days prior to study intervention.
 
 7. Female participants of child bearing potential and male participants whose partner is of child bearing potential who are not willing to practice an acceptable form of contraception (i.e. oral contraceptive, diaphragm, cervical cap, condom, surgical sterility) during the study and for 6 months thereafter. Women whose partner has or men who have undergone a vasectomy must use a second form of birth control. 8. Have any known allergic reactions to any of the drugs or liposomal components or intravenous imaging agents to be used in this study. 9. Have portal or hepatic vein tumour invasion/thrombosis. 10. Inadequate haematological and biochemical function (section 4.1.2) 11. Have contraindications to receiving doxorubicin including prior sensitivity (rash, dyspnoea, wheezing, urticarial or other symptoms) attributed to anthracyclines or other liposomal drugs. 12. Use of chemotherapy or of an investigational drug within 30 days or 5 half-lives, whichever is longer, preceding the intervention. 13. Have medically significant active infection. 14. Have Child-Pugh Class C liver disease, or Class A-B with encephalopathy and/or refractory ascites (Appendix 3). 15. Documented HIV positive. 16. Documented diagnosis of haemochromatosis. 17. Documented history of contrast-induced nephropathy. 18. Have any of the following contraindications for liver biopsy: 
 a. Suspected liver haemangioma or other vascular tumour b. Tense ascites c. Known cystic liver disease* d. Extra-hepatic biliary obstruction* 
(* Relative contraindications only and may be non-exclusive at discretion of the study team)
 19. Other medical or psychiatric conditions or laboratory abnormalities that the investigator considers would make the patient a poor trial candidate.
Trial dose and administration:	
The investigative medicinal product is ThermoDox® LTSL doxorubicin. It is supplied in 20cc vials each vial containing 30mg doxorubicin in 15ml of solution. A carton containing 4 vials is normally sufficient for one treatment of one subject.
 
One single dose of ThermoDox® with a doxorubicin concentration of 50mg/m² will be given during the FUS exposure session as an intravenous infusion for both Part I & II.

Duration on study:	30 days from intervention (Day 1) with a maximum of 60 days of radiological follow-up

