Study Procedures and frequency:	
Part I
 
Part I is concerned with optimisation of the FUS acoustic parameters. The optimal FUS exposure parameters to achieve the desired range of mild hyperthermia in the target tumour (and consequent ThermoDox® release) will be determined. A single target liver tumour will have already been identified. The participant requires insertion of a co-axial needle during intervention for monitoring and biopsy; consequently Part I is minimally invasive.
 
Day -1: Attend for oral premedication and for baseline radiological assessment (Liver MRI/MR-Spectroscopy, Liver pCT and whole body FDG PET-CT scans)
 
Day 1: Target tumour exposed to a combination of FUS and ThermoDox® under General Anaesthetic. Three liver tumour biopsies and temperature readings are taken via a single co-axial needle. Three peripheral blood samples are taken for

		
plasma pharmacokinetics.
 
Day 2: Peripheral blood samples (FBC, U&E, LFT) are taken. Repeat Liver MRI/MR-Spectroscopy is performed within 36 hours of intervention. Participant is discharged after a minimum of 24 hours of observation post-intervention.
 
Follow-up: Clinical reviews and repeat set of blood samples (FBC, U&E, LFT) at Days 15 and 30. A maximum of two further sets of scans (Liver MRI/MR-Spectroscopy, Liver pCT and whole body FDG PET-CT) are performed within 60 days post-intervention (one at 4 week follow-up, the other being flexible).
 
Part II
 
Part II is concerned with monitoring efficacy of the intervention (ThermoDox® release by mild hyperthermia), using the optimised FUS acoustic parameters identified in Part I. In particular, the release of doxorubicin and its therapeutic effect will be investigated. A single liver tumour will have been identified for intervention.. The participant requires insertion of a co-axial needle during intervention for a biopsy of the tumour area receiving FUS exposure for HPLC and microscopy analysis, and consequently Part II is minimally invasive.
 
Day -1: As for Part I.
 
Day 1: Target tumour exposed to a combination of FUS and ThermoDox® under General Anaesthetic. Two biopsies of the tumour receiving intervention are taken via a single co-axial needle. Peripheral blood samples are taken for plasma pharmacokinetics.
 
Day 2: As for Part I.
 
Follow-up: As for Part I.

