To assess the safety of FUS-induced mild hyperthermia for drug delivery	1. Persistence of cell viability stain or percentage of cell or tissue necrosis under 30% following FUS exposure, as assessed by cytological or histological	1. Cytological or histological analysis of biopsy samples processed within 96hr of intervention†

	methods ¹⁶ ‡,§ 2. Adverse events deemed related to FUS up to 30 days post-intervention	2. Adverse event recording for 30 days post-intervention
To assess the local and systemic cytotoxic effects of ThermoDox® in this setting	1. Significant bone marrow suppression, deranged liver function and liver toxicity 2. Adverse events deemed related to ThermoDox® up to 30 days post-intervention	1. Grade 3 and 4 laboratory results from blood tests at Day 1 and Day 15 post intervention 2. Adverse event recording for 30 days post-intervention

Table 2: Secondary Objectives and Endpoints for Parts I & II of the TARDOX Study

Regarding participants for which doxorubicin has been released by optimal FUS exposure parameters:

Tertiary (Exploratory) Objectives	Tertiary (Exploratory) Endpoints	How and when data is captured
1. To establish the validity of other minimally-invasive and non-invasive methods of evaluating intratumoural uptake of doxorubicin as an alternative to that used in primary endpoint	Combined analysis of relevant end points to establish most effective alternative analytical method(s) for quantifying drug release	See below
a. Fluorescence microscopy of biopsy	Released biopsy samples exhibiting regions of nuclear or background fluorescence levels at least twice that of a suitable control, as assessed by fluorescence microscopy ‡,§	Microscopic analysis of biopsy samples processed within 96hr of intervention†
b. MR-Spectroscopy	Liver MRI/MR-Spectroscopy indicating ¹⁷ targeted delivery of doxorubicin to the tumour by demonstrating a statistically significant increase in the tumour:background ratio of signal intensity following intervention compared to baseline	MRI/MR-Spectroscopy signal within 36 hours of intervention
c. Plasma pharmacokinetics	A statistically significant decrease in total doxorubicin plasma levels over time-matched clearance levels, following HIFU-induced release	Analytical chemistry of plasma samples processed within 12hr of intervention†

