7. Female participants of child bearing potential and male participants whose partner is of child bearing potential who are not willing to practice an acceptable form of contraception (i.e. oral contraceptive, diaphragm, cervical cap, condom, surgical sterility) during the study and for 6 months thereafter. Women whose partner has or men who have undergone a vasectomy must use a second form of birth control.
8. Have any known allergic reactions to any of the drugs or liposomal components or intravenous imaging agents to be used in this study.
9. Have portal or hepatic vein tumour invasion/thrombosis.
10. Inadequate Haematological and Biochemical indices:

Lab Test	Exclude if:
INR	> 1.5 times the institution's upper normal limit (UNL)*
Absolute neutrophil count	$< 1,500/\text{mm}^3$ (or $< 1.5 (10^9/\text{L})$)
Platelet count	$< 60,000/\text{mm}^3$ (or $< 60 (10^9/\text{L})$)
Hgb	$< 9.0 \text{ g/dL}^{**}$
Serum creatinine, or Calculated creatinine clearance (CrCl)	$\geq 2.5 \text{ mg/dL}$ (or $\geq 221 \mu\text{mol/L}$) $\leq 25.0 \text{ mL/min.}$
Serum bilirubin	$> 3.0 \text{ mg/dL}$ (or $> 51 \mu\text{mol/L}$)

Serum albumin	< 2.8 g/dL (or <28 g/L)
---------------	-------------------------

* Except in patients who are therapeutically anticoagulated for medical conditions unrelated to cancer such as atrial fibrillation. Subjects may be re-screened after the condition is treated or anticoagulant is withheld

** Unless the haemoglobin value has been stable, the patient is cardiovascularly stable, asymptomatic, and judged to withstand the FUS procedure

11. Have contraindications to receiving doxorubicin including prior sensitivity (rash, dyspnoea, wheezing, urticarial or other symptoms) attributed to anthracyclines or other liposomal drugs.
12. Use of chemotherapy or of an investigational drug within 30 days or 5 half-lives, whichever is longer, preceding the intervention.
13. Have medically significant active infection.
14. Have Child-Pugh Class C liver disease, or Class A-B with encephalopathy and/or refractory ascites (Appendix 3).
15. Documented HIV positive.
16. Documented diagnosis of haemochromatosis.
17. Documented history of contrast-induced nephropathy.
18. Have any of the following contraindications for liver biopsy:
 - a. Suspected liver haemangioma or other vascular tumour
 - b. Tense ascites
 - c. Known cystic liver disease*
 - d. Extra-hepatic biliary obstruction*

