5.2 Evaluations during the intervention (d-1 to d2)

Evaluations on day -1 (pre-Intervention day)

- Dose of oral dexamethasone given as pre-medication (section 5.5.2 & 9.3)
- Baseline scans (Usually on d-1 but may be performed from day -7 to day 1 provided before intervention):
 - Liver MRI/MR -Spectroscopy
 - Liver pCT

- Whole body FDG PET-CT

Evaluations on day 1 (intervention day)

- Confirm d-1 pre-medications were given.
- Day 1 pre-medications given
- Confirmatory portable ultrasound to confirm tumour location before patient anaesthetised
- General anaesthetic start and finish time
- Dose of ThermoDox® administered, start and finish time
- Start and finish time of final FUS exposure and FUS parameters
- Thermometry data (Part I only)
- Bloods samples for pharmacokinetics (Pre-Treatment, Unreleased and Released plasma samples)
- Biopsy samples for assay quantification \pm microscopy:
 - Part I: Pre-Treatment, Unreleased, Released
 - Part II: Released
- Adverse event monitoring

Evaluations on day 2 (recovery day)

- Physical exam
- Vital signs: Temperature, resting pulse and blood pressure (BP) after participant has been in a sitting position for at least five minutes
- Full Blood Count (FBC); including Haemoglobin (Hb), white blood cells (WBC) with differential count (neutrophils and lymphocytes), and platelets
- Biochemical profile; including sodium, potassium, calcium, phosphate, urea, creatinine
- Liver profile; including total protein, albumin, bilirubin, ALP, AST and/or ALT and LDH
- Post-treatment Liver MRI/MR-Spectroscopy (within 36 hours, and ideally within 24 hours, of intervention¹⁸)
- Adverse event monitoring

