5.3 Follow-up and end of study evaluations (within 60 days)

Follow-up 1: Day 15 (± 3 day tolerance)

Parts I & II:

- Full Blood Count (FBC); including Haemoglobin (Hb), white blood cells (WBC) with differential count (neutrophils and lymphocytes), and platelets
- Biochemical profile; including sodium, potassium, calcium, phosphate, urea, creatinine
- Liver profile; including total protein, albumin, bilirubin, ALP, AST and/or ALT and LDH
- Adverse event monitoring

Follow-up 2: Day 30 (+7 not <30)

Parts I & II:

- Adverse event monitoring
- Concomitant medication recording
- Full Blood Count (FBC); including Haemoglobin (Hb), white blood cells (WBC) with differential count (neutrophils and lymphocytes), and platelets
- Biochemical profile; including sodium, potassium, calcium, phosphate, urea, creatinine
- Liver profile; including total protein, albumin, bilirubin, ALP, AST and/or ALT and LDH

Follow-up Scans: From Day 12 - Day 60 post-intervention as defined in the summary of schedule events (one set of scans at 4 weeks follow-up, the other being flexibly timed in accordance with emerging radiological data from previous study participants)

Parts I & II:

- Maximum of two follow-up Liver MRI/MR-Spectroscopy scans
- Maximum of two follow-up Liver pCT scans
- Maximum of two follow-up whole body FDG PET-CT scans

¹⁸ The time of intervention is defined as the time at which the final FUS exposure is complete

If a participant is withdrawn from the study following the intervention, adverse event recording should continue for 30 days post-intervention. No other follow-up evaluations will be required.

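### The capture days that Table 2 gives for the laboratory toxicity endpoint do not match the blood-test schedule, and Day 30 is left out on any reading

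*Protocol*

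**What the plan says.** The synopsis lists the secondary endpoint as "Significant bone marrow suppression, deranged liver function and liver toxicity" and gives no time point. Table 2 in section 3 supplies one. Under the objective on local and systemic cytotoxic effects of ThermoDox, this endpoint is captured from "Grade 3 and 4 laboratory results from blood tests at Day 1 and Day 15 post intervention". The second endpoint for the same objective is adverse events attributed to ThermoDox, recorded for 30 days.

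The protocol's day count starts at the intervention. The synopsis gives the duration on study as "30 days from intervention (Day 1) with a maximum of 60 days of radiological follow-up", and section 5.2 uses the heading "Evaluations on day 1 (intervention day". The blood samples listed under that heading are the three pharmacokinetic plasma samples. Full blood count, biochemistry and liver profile appear under the next heading, "Evaluations on day 2 (recovery day". They appear again in section 5.3 at Day 15 and at "Follow-up 2: Day 30 (+7 not <30". The synopsis agrees: Day 2 bloods, then "Clinical reviews and repeat set of blood samples" at Days 15 and 30. The haematology and biochemistry rows of the schedule of events are marked at screening, Day 2, Day 15 and Day 30, and are blank at Day 1.

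**The concern.** Table 2 is where the protocol turns a general safety aim into a countable endpoint, and the days it names are not the days on which the tests are done. An analysis plan that follows the cell literally looks for a Day 1 toxicity panel that is not scheduled, and ignores Day 30. One that uses all the scheduled bloods departs from the protocol's definition. This is not a detail left for later, because the protocol fixes the days itself.

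The Day 30 omission matters most. For this objective, the laboratory endpoint is the one that rests on measured values and not on an investigator's attribution. It stops at Day 15, while its companion, which needs a judgement of relatedness in an open-label single-arm study, continues to 30 days. Late-appearing marrow or liver abnormality is then seen only through that judgement.

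**Working it through.** The protocol states no statistical figure on this point, so the check compares the places that name a day.

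| Source | Post-intervention haematology and biochemistry |
|---|---|
| Synopsis, study procedures | Day 2, Day 15, Day 30 |
| Schedule of events | Day 2, Day 15, Day 30 |
| Sections 5.2 and 5.3 | Day 2, Day 15, Day 30 |
| Section 3, Table 2 | Day 1, Day 15 |

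**Step 1, literal reading.** Day 1 is the intervention day. The scheduled set is {2, 15, 30} and the Table 2 set is {1, 15}. The only common day is 15. Day 1 is named but has no such test. Days 2 and 30 have the test but are not named.

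**Step 2, lenient reading.** Suppose Table 2 counts days after the intervention.
- Day 1 post intervention = study day 1 + 1 = 2, which is scheduled.
- Day 15 post intervention = study day 1 + 15 = 16. This is not the nominal day, but it lies in the Day 15 window of ±3 days (15 − 3 = 12 to 15 + 3 = 18).
- Day 30 is still not named.

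The lenient reading therefore restores Day 2 and leaves Day 30 out.

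**Step 3, size on the lenient reading.** Each participant has 3 scheduled post-intervention draws. With the maximum of 28 evaluable participants (section 16.1), 28 × 3 = 84 draws. Day 30 accounts for 28 × 1 = 28, so 28 / 84 = one third are outside the endpoint. Section 6.1 replaces non-evaluable patients, and section 17.1 makes all patients evaluable for toxicity from their intervention. The number treated could therefore exceed 28, but the fraction would not change.

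**Step 4, what the other route catches.** Follow a result first seen at the Day 30 visit.
- Grade 4: section 13.2 requires it to be reported as an SAE, so it is always visible. It enters the companion endpoint if attributed to ThermoDox.
- Grade 3, judged clinically significant and attributed to ThermoDox: recorded as an adverse event and counted in the companion endpoint.
- Grade 3, judged clinically significant but not drug-related: recorded as an adverse event, but not counted in the companion endpoint.
- Grade 3, judged not clinically significant: section 13.2 does not make it an adverse event, so it is counted nowhere.

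The last two cases fall outside both endpoints for this objective.

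**The case against.** The best defence is that this is an off-by-one label. The Table 2 cell speaks of days post intervention, the day after the intervention is study Day 2, and a full toxicity panel is scheduled then. That reading makes sense of the cell and is probably what was meant. A reader might infer from the literal text that two of three draws, 28 × 2 = 56 of 84, are left out. The documents do not support that figure, because it depends on the less plausible reading.

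Second, Day 30 toxicity is not lost. The bloods are drawn, adverse event monitoring runs to the Day 30 visit (section 13), Grade 4 results are SAEs, and section 17.1 tabulates treatment-related toxicity by worst grade. A Grade 3 or 4 toxicity already present at Day 15 and unresolved at Day 30 is counted from the Day 15 sample. This stands, and it narrows the gap to the Grade 3 cases in the last two lines of the working.

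Third, an early sample and a mid-cycle sample might be a deliberate choice. Section 8.12 places myelosuppression at 10–15 days, which overlaps the Day 15 window. But that statement concerns overdose, and the protocol does not give it as the reason for the days in Table 2.

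A reader might also infer that the endpoint counts abnormalities already present at entry, since section 4.1.2 waives the haemoglobin limit in some cases ("Unless the haemoglobin value has been stable") and admits platelets down to 60 × 10⁹/L and bilirubin up to 51 µmol/L. The documents do not carry that point. They give no CTCAE cut-offs showing that platelet or bilirubin values at those limits are Grade 3. Rules for worsening from baseline, and shift tables, are ordinary content of the analysis plan, which is not at hand.

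**Conclusion.** The point holds as a contradiction within the protocol that should be fixed. Table 2 disagrees with three other parts of the document about when the laboratory endpoint is measured, and it omits the Day 30 bloods on either reading. If Day 1 means one day after the intervention, the omission is one of three scheduled draws per participant, up to 28 of 84. That is a count of scheduled samples with full attendance assumed, not an estimate of missed toxicity.

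The practical effect is limited. What can escape both endpoints for this objective is mainly a Grade 3 result first seen at Day 30 and judged not clinically significant or not drug-related. The documents give no basis for saying how often that would happen. The primary endpoint is unaffected, and the protocol ties no decision threshold to this laboratory endpoint.

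**What to change.** Reconcile Table 2 with the schedule. Replace the capture days with the worst CTCAE grade over the scheduled Day 2, Day 15 and Day 30 bloods, in the study-day numbering used elsewhere. Refer to the visits with their windows, because the Day 30 visit may fall up to seven days later and its sample should still count. The analysis plan should use the same definition.

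The cost is one table cell and its counterpart in the analysis plan. No visit or blood draw is added, because all three samples are already required.

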8.12 Management of overdose

Acute overdose of ThermoDox® and thus doxorubicin may lead to acute cardiac alterations within twenty-four hours and myelosuppression usually 10-15 days following overdose. Urgent medical attention must be sought for which treatment will vary depending on the circumstances, but may involve reverse barrier nursing, intravenous antibiotics, transfusion of blood products, symptomatic treatment of mucositis and cardiology input. More information can be found in Appendix 1 of the ThermoDox® IB [44].

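### Table 2 takes the laboratory toxicity endpoint from Day 1 and Day 15, but safety bloods are scheduled on Days 2, 15 and 30, so the Day 30 panel is left out

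*Protocol*

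**What the plan says.** Section 3, Table 2, sets two endpoints against the objective on local and systemic cytotoxic effects of ThermoDox. The first is "Significant bone marrow suppression, deranged liver function and liver toxicity", and its capture column reads "Grade 3 and 4 laboratory results from blood tests at Day 1 and Day 15 post intervention". The second, in the same row, is ThermoDox-related adverse events, recorded for 30 days after the intervention.

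The blood-sampling schedule is stated elsewhere:

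- **Day numbering.** The synopsis gives the time on study as "30 days from intervention (Day 1) with a maximum of 60 days of radiological follow-up", so the intervention day is Day 1.
- **Day 1.** The only bloods in section 5.2 are "Bloods samples for pharmacokinetics (Pre-Treatment, Unreleased and Released plasma samples").
- **Day 2.** The synopsis says "Peripheral blood samples (FBC, U&E, LFT) are taken". Section 5.2 lists the full blood count, biochemical profile and liver profile under the recovery day.
- **Days 15 and 30.** The synopsis says "Clinical reviews and repeat set of blood samples (FBC, U&E, LFT) at Days 15 and 30". Section 5.3 repeats all three panels under Day 15 (±3) and under "Follow-up 2: Day 30 (+7 not <30").

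The synopsis also lists this endpoint among the secondary endpoints but names no days for it.

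**The concern.** The capture column is where the protocol fixes which results feed the endpoint. An analyst who follows it would look for a Day 1 safety panel that is not scheduled, and would set aside a Day 30 panel that the schedule requires for every participant. The row would also carry two observation windows for one objective: 30 days for related adverse events, but only to Day 15 for laboratory grades.

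This is a secondary safety endpoint of a Phase 1 study. Leaving out samples already drawn can only lower the Grade 3 and 4 count or leave it unchanged.

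**Working it through.** No sample size, power or error rate is involved, and the protocol states no figure to reproduce. The check is a comparison of days.

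**1. Days on which safety bloods are drawn after the intervention**

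| Source | Day 1 | Day 2 | Day 15 | Day 30 |
|---|---|---|---|---|
| Synopsis, study procedures | PK plasma only | yes | yes | yes |
| Schedule of events | PK plasma only | yes | yes (±3) | yes (+7) |
| Sections 5.2 and 5.3 | PK plasma only | yes | yes (±3) | yes (+7) |
| Table 2, read as study days | named | not named | named | not named |
| Table 2, Day 1 read as one day after | – | named | named | not named |

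**2. Study-day reading.** The schedule gives {2, 15, 30} and Table 2 gives {1, 15}. Only Day 15 is common to both. Table 2 names one day without safety bloods and omits two days that have them.

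**3. Elapsed-day reading.** One day after the intervention is study Day 1 + 1 = Day 2, when a panel is drawn. Counted the same way, 15 days after is study Day 16. That is not the scheduled label, although it lies inside the window of Days 12 to 18. The phrase therefore mixes two day counts or mislabels one day. Taken generously the set is {2, 15}, and Day 30 is still missing.

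**4. What the other routes catch.** Section 13 monitors adverse events from the intervention to the Day 30 visit. Section 13.2 has all Grade 4 laboratory abnormalities reported as SAEs, and records other abnormal results as AEs or SAEs where the investigator judges them clinically significant and they meet the definitions. Section 17.1 tabulates treatment-related toxicity by grade, including the worst grade.

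**5. What remains uncounted.** After step 4, the values that reach neither the laboratory endpoint nor the adverse event tables are mainly Grade 3 results that are not judged clinically significant and are first seen at Day 30. Read literally, Table 2 also leaves out unscheduled samples. Section 13.9 foresees such samples, since patients with adverse events have further laboratory tests at the investigator's discretion.

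**6. Size.** With the maximum of 28 evaluable participants as denominator, each participant missed in this way lowers the endpoint's rate by 1/28 = 3.6 percentage points. The protocol gives no figure for how many Grade 3 values would appear first at Day 30 or on an unscheduled sample, so no expected loss can be calculated.

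**The case against.** The strongest reply is that this is a wording slip in one table cell with little effect. Day 1 followed by a reference to post-intervention plausibly means the next day, study Day 2, when the panel is drawn. The adverse event and SAE routes run to the Day 30 visit and pick up every Grade 4 value and every clinically significant abnormality. The synopsis version of the endpoint excludes no day. No stopping rule or test uses the endpoint, and Part II opens on a review of thermometry (sections 2 and 17.3). Derivation details may sit in the statistical analysis plan, which is not at hand.

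Most of this stands, and it limits the severity. It does not remove the point. The omission of Day 30 survives the generous reading of Day 1. The adverse event route depends on clinical judgement for Grade 3 values, whereas the laboratory endpoint counts by grade. Because Table 2 itself names the days, an analysis plan that counted Day 30 would depart from the protocol rather than fill a gap in it.

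Three stronger readings are tempting but not supported:

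- **That marrow toxicity will be missed.** The protocol's only timing, "myelosuppression usually 10-15 days following overdose", comes from the overdose section. The Day 15 window of study Days 12 to 18, or 11 to 17 days after dosing, overlaps it in any case. The endpoint also covers liver toxicity, so a Day 2 draw is not pointless.
- **That a known share of cases is lost.** Table 7 lists 65 neutropenia cases among 354 patients. That is 65/354 = 18.4%, while the table prints 18.9%. The population is hepatocellular carcinoma treated with radiofrequency ablation, and section 13.4 itself warns that this study's population differs. Nothing there says when such cases appear.
- **That serious toxicity goes unreported.** Sections 13 and 13.2 show otherwise.

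**Conclusion.** The point holds as an internal inconsistency with a limited effect. Table 2 and the schedule disagree on the days that feed the laboratory toxicity endpoint, and the Day 30 panel is omitted whichever way Day 1 is read. Whether a Day 1 safety draw is truly called for but unscheduled, or Day 2 is simply mislabelled, cannot be settled from the protocol.

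Any bias in the endpoint is downward. It is confined mainly to Grade 3 values that are first seen at Day 30, or on an unscheduled sample under a literal reading, and are not judged clinically significant. Its size cannot be derived. The conclusion assumes that the capture column will be applied as written and that section 13.2 is followed for Grade 4 and clinically significant values. Severity is low to moderate: worth correcting because the rule as written is wrong and the correction is cheap, but not a threat to participants' safety reporting or to the primary endpoint.

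**What to change.** Amend the capture cell in Table 2 so that the endpoint counts Grade 3 and 4 results from all post-intervention haematology, biochemistry and liver panels through the Day 30 (+7) visit: Days 2, 15 and 30, plus any unscheduled samples in that window. Use the study-day numbering of the schedule throughout, with the intervention as Day 1. How the results are then summarised can be left to the statistical analysis plan.

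The cost is one line of text in a protocol amendment. No additional sample or visit is needed, because the scheduled bloods are already drawn. The downside is that the reported Grade 3 and 4 rate may rise slightly.
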